## 12.8 \* Secondary Outcome(s)

Indicate which **additional variable(s)** will be assessed to judge the secondary outcome(s). Give measurement units, if applicable.

- a. Gene expression profiles in the mucosa and submucosa compartments in humans before and after course of antibiotics.
- b. Gut microbiota changes in humans after course of antibiotics.
- c. Gut metabolites changes in humans after course of antibiotics.

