**VISIT #5: Procedure Visit (21 to 30 days after Visit #4) (approximately 2 hours; Day Patient Visit)**

- Stool sample will be collected and stored in the refrigerator.

- Vital signs pre- and post-procedure. Post-procedure, vital signs will be taken immediately after the procedure, then 30 minutes after the procedure, and 1hr after the procedure.
- POC Urine Pregnancy test for women of childbearing age.
- Stool consistency and frequency questionnaire will be given to the participant to complete.
- Oral diazepam 5 mg pre-procedure will be offered and administered based on the patient preference and PI evaluation. Oral diazepam takes 30 - 60 minutes to take effect.
- Tap water enema upon arrival followed by additional 1 or 2, 200ml tap water enemas if the participant still has solid debris after a bowel movement.
- Flexible Sigmoidoscopy Procedure
- The sigmoidoscope is advanced to the beginning of the descending colon (about 24 cm) and up to 20 biopsies will be obtained with Boston Scientific Jumbo forceps (max diameter of 2.8mm), each biopsy will be 2-2.8 mm in size, one in each quadrant, spaced 2-3cm throughout the sigmoid colon.
- Tissue specimens will be placed in sterile specimen cups containing normal saline.
- Observation for one-hour post-procedure (for signs of bleeding or distress) and evaluation by nursing and PI to determine when ready for discharge.
- Breakfast
- Post-procedure Instruction sheet given prior to departure.
- In the event a mass, polyp, or ulceration is found, a copy of the images obtained during the sigmoidoscopy and a letter with the examination findings will be given to the participant and they will be instructed to follow-up with their Primary Healthcare Provider.

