#### Lab Procedures

Sample processing and analysis.

A total of 20 biopsies will be obtained per participant: 4 will be used for tissue immunostaining and remaining 16 will be used for single nuclei sequencing. Tissue obtained from each region will be separated: four biopsies will be pinned and fixed in 4% paraformaldehyde overnight, followed by washing, permeabilization, and staining of the tissue with the neuronal antibody ANNA-1 and anti-Sox10 which is a glia antibody. We will image the samples with a confocal microscope, and we will count the neurons and glia. Sixteen biopsies will be snap frozen in liquid nitrogen and stored in a -80C freezer. Once several samples have been collected, we will defrost them and further process them into single nuclei suspensions that will be utilized to generate sequencing libraries with the 10X Chromium platform. We will sequence the nuclear RNA to determine the expression of multiple genes in the human intestine. Of note, we do not know what the nuclei yield will be for the pooled 16 biopsies obtained per participant, our target nuclei count will be about 20,000 in total. We will enrich the desired populations by staining the nuclei with anti-NeuN and anti-Sox10 to sort the neurons and glia populations respectively. We do not know what will be the proportions of the different cell types for this particular protocol, however, based on other studies we expect small proportion of glia and neurons thus making it necessary to pool samples from several participants. We will not sequence the human DNA. We will isolate bacterial DNA from the stool and perform 16S ribosomal RNA sequencing for which we have an optimized protocol in our lab. Moreover, we will identify and measure stool metabolites via Liquid Chromatography- Mass Spectrometry at RU Proteomics Core.

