**12.10 \* Data Analysis**

Describe method(s) of data analysis.

In this pilot study, with 10 participants, we will assess the change in the outcomes between baseline and follow up using a paired sample t-test. While exploratory, we will be able to detect a 1.3 standard deviation change in outcomes pre versus post, with greater than 80% power, holding Type I Error to 5%.

**12.11 \* Explain the rationale for the choice of statistical measures and the number of participants proposed for the study, including the power calculations when applicable.**

Assuming we can enroll 10 patients, we will have over 80% power to detect a 1.3 standard deviation difference in continuous outcome measures and a 38% absolute difference in proportions (assume base rate of 50%). This pilot study will also provide observed effect size for use in the design of future analysis.

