#### **Projected Time to Accrual Completion (PTAC):**

The research team plans to screen up to 1 day per week which translates to enrolling 2 volunteers a week.

Factors Affecting Predicted Time to Accrual Completion	Weeks
Research team plans to screen 2 participants 1 day per week = 2 volunteers screened per week (10 pax Add 2 weeks for overlap with current study, YAL-1027	11
Anticipated start up, add 1 2 weeks; if assay not ready, add estimated time to readiness	1
Add any vacation time when screen/visit capacity will be reduced	1
Recruitment is to occur during August? add 2 weeks due to historical slowing	N/A
Recruitment to occur across Dec Jan. time frame; add 2 wks for unit closure	N/A
Known anticipated maternity leave, other LOA of key staff – add est. weeks lost capacity	N/A
Staff or KSP changes – add onboarding time	N/A
Staff travel for major conferences – add weeks lost capacity	N/A
Institutional interruptions (graduation, symposium days, etc.) add team estimate	N/A
Projected Time to Accrual Completion (PTAC)	13

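### Sequencing runs are not required to hold a participant's before and after samples together, so run differences can be partly confounded with visit in the gene expression outcome

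*Combined protocol and SAP*

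**What the plan says.** Under Lab Procedures in Section 12.9, each procedure visit yields up to 20 biopsies. Four are fixed for immunostaining and 16 go to single-nuclei sequencing. For the latter, "Sixteen biopsies will be snap frozen in liquid nitrogen and stored in a -80C freezer". Processing then begins on a trigger: "Once several samples have been collected, we will defrost them and further process them into single nuclei suspensions". The same paragraph expects few neurons and glia, "thus making it necessary to pool samples from several participants".

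The outcome served is secondary outcome (a) in Section 12.8: "Gene expression profiles in the mucosa and submucosa compartments in humans before and after course of antibiotics". For the analysis, Section 12.10 says only that "we will assess the change in the outcomes between baseline and follow up using a paired sample t-test", with type I error held at 5%. It does not say whether follow-up means Visit 4 or Visit 5. Section 36.3 selects no RNA-seq method.

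Nowhere does the plan say how many samples make a run, in what order they are taken, whether a participant's visits stay together, or how run enters the analysis.

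**The concern.** A paired comparison removes whatever the two samples of a pair share. If a participant's Visit 2 and follow-up samples are thawed, sorted and sequenced in different runs, the run is not shared, and its effect stays in the difference. Where many participants have their baseline in early runs and their follow-up in later ones, those effects do not average out: they shift the mean change in one direction, as an antibiotic effect would.

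An accumulation trigger leaves room for this because the visits are weeks apart. The cost would be genes reported as changed because of processing. Section 12.11 also intends the observed effect sizes to inform later studies, so a biased change would carry forward.

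**Working it through.** **The plan's own figures.** None concerns batching. The power statement in Section 12.10 (1.3 SD, 10 participants, over 80%) is true for a paired t-test: two-sided noncentral-t power is 95.4%. It presumes no run effect and does not settle this point. The figure under test is the 5% type I error.

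**Visit spacing (Section 12.9).** Visit 3 is 14-21 days after Visit 2. Visit 4 is 5-9 days after antibiotics start (assumed to be the day of Visit 3). Visit 5 is 21-30 days after Visit 4.
- Visit 2 to Visit 4: 14 + 5 = 19 to 21 + 9 = 30 days.
- Visit 2 to Visit 5: 19 + 21 = 40 to 30 + 30 = 60 days.

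**Accrual (Section 17.1).** The plan is one screening day a week, "which translates to enrolling 2 volunteers a week". At that pace, 2 × 19/7 = 5.4 to 2 × 30/7 = 8.6 baseline samples accumulate in the time one participant takes to reach Visit 4.

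**Model.** For participant i, change = true effect + (run effect of the follow-up sample − run effect of the Visit 2 sample) + error. If both samples share a run, the bracket is zero.

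**Assumptions not in the documents.** Runs of 6 or 10 samples, filled strictly in collection order. The difference between two runs has SD 0.5 of the paired-change SD, so each run's effect has SD 0.5/√2 = 0.35. The generic paired t-test is applied to a gene with no true change (two-sided, 9 df), and visit dates are drawn from the stated windows. Participants' profiles are assumed to remain separable after pooling.

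**Simulated false-positive rate, nominal 5%:**

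| Accrual | Visit 4 vs 2 | Visit 5 vs 2 |
|---|---|---|
| 2 a week | 8-13% | 12-20% |
| 1 a week | 4-7% | 9-15% |
| 1 per 4 weeks | about 5% | about 5% |

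At two a week, a participant's Visit 2 and Visit 4 samples share a run in about 2% of cases (runs of 6) or 19% (runs of 10). Visit 2 and Visit 5 samples never do, which is why that contrast is worse. At one per four weeks, 60-85% of the Visit 2/Visit 4 pairs share a run.

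**Sensitivity to the run SD** (two a week, runs of 6). With run-difference SD 0.25, 0.5 and 1.0, the rates are 6%, 10% and 17% for Visit 4 vs 2, and 8%, 13% and 27% for Visit 5 vs 2. If 0.5 is taken as the SD of each run rather than of the difference (0.5 × √2 = 0.71), the rates over runs of 6 or 10 are 12-17% and 21-29%.

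**Upper bound.** If all ten baselines sat in one run and all ten follow-ups in another, one shift would be common to every pair. The rate would then be 2·P(t₉ > 2.262/√(1 + 10s²)), with s the run-difference SD: 11.0%, 25.7% and 51.2% for s = 0.25, 0.5 and 1.0. Runs of 6 cannot produce this, since ten baselines do not fit in one.

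**Under the remedy.** With all three visits of a participant in one run, the bracket cancels and the simulated rate (Visit 4 vs 2) is 4.4-5.0% at every run SD tried. Randomising samples to runs gives 4.2-5.8%, but leaves run noise in the paired differences.

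**The case against.** The strongest reply is that the plan gives a trigger, not an order. Tissue at -80C can be grouped in any way, including by complete participant, and the laboratory may do so. That stands: a reader might infer that runs fill in visit order and that run differences will be reported as antibiotic effects, but the documents say neither. Even strict collection order mixes visits, because entry is staggered. At two a week, 44-65% of the runs holding Visit 2 or Visit 4 samples contain both.

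Accrual was also probably slower than two a week. Section 17.1 describes screening capacity. Sections 13.6 and 13.7 plan 20 consents for 10 evaluable participants, which halves the rate to about one a week. Section 17.2 allows 12 months, or 52/10 ≈ one per five weeks. From IRB approval on 12/01/2022 to closure on May 24, 2024 is 540 days, about 77 weeks, or one per 7.7 weeks if spread evenly (an assumption). At such a pace, collection-order runs show little or no inflation.

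The stakes are bounded too. The outcome is secondary, the analysis is labelled exploratory, and the primary cell counts come from separately fixed biopsies outside this freeze-thaw step. The plan specifies no gene-by-gene test, and pooling across participants may leave fewer than ten separable pairs.

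These points limit the size and certainty of the problem. They do not close the gap: protection now rests on accrual speed and on a laboratory choice that the plan does not record.

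**Conclusion.** The concern holds as a risk that the plan leaves unguarded. Nothing keeps a participant's three visits in one run, and the stated test cannot absorb a run effect, so run and visit can be partly confounded in secondary outcome (a). Under the assumed batching, the inflation ranges from none at slow accrual to a false-positive rate of up to about 20% for Visit 5 vs 2 at two participants a week. Run size, run SD and collection-order filling are all assumptions; the documents fix none of them.

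A reader might go further and quote 26% or 51% false positives. Those rates need complete confounding, which nothing in the plan prescribes. Nor do the documents support extending the point to the primary counts, or to the 16S and metabolite assays: the quoted trigger concerns the frozen biopsies only. This is a change worth making, not a threat to the primary result.

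**What to change.** Replace the trigger sentence in Section 12.9 with:

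> Frozen biopsies are held at -80C until the participant's last procedure; each participant's Visit 2, 4 and 5 samples are thawed, sorted, made into libraries and sequenced in the same run, in randomised order, and the run is recorded.

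Add that any pooling across participants is balanced across visits, so that each visit's pool draws on the same people.

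Enrolment closed on May 24, 2024, so some or all samples may already have been processed. In that case, report the composition of each run by visit and include run in the analysis where it can be estimated. Where run and visit coincide it cannot be, and the report should say so.

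The cost is a delay of up to about 60 days before a participant's first sample is processed, and no delay for samples whose donor has already finished. The freezing step is already planned, and no further biopsies are needed. The rule removes a run effect common to the three visits. It does not remove differences in storage time, since Visit 2 tissue will have been frozen 40-60 days longer than Visit 5 tissue, so storage time should be recorded as well.

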#### NOTE:

This study will follow the NYSDOH guidelines regarding COVID-19 testing throughout the course of the study. Any participant that reports experiencing COVID symptoms and has a positive SARS-Cov-2 PCR test will not be able to undergo the flexible sigmoidoscopy procedures until 5 days after symptom onset provided that symptoms are resolved. For example, if a participant develops COVID while taking antibiotics, he/she will have to wait until symptom resolution to undergo follow up flexible sigmoidoscopy.

We will also follow RU COVID-19 clinic policies.

Study is closed to enrollment as of May 24, 2024.

**12.10 \* Data Analysis**

Describe method(s) of data analysis.

In this pilot study, with 10 participants, we will assess the change in the outcomes between baseline and follow up using a paired sample t-test. While exploratory, we will be able to detect a 1.3 standard deviation change in outcomes pre versus post, with greater than 80% power, holding Type I Error to 5%.

**12.11 \* Explain the rationale for the choice of statistical measures and the number of participants proposed for the study, including the power calculations when applicable.**

Assuming we can enroll 10 patients, we will have over 80% power to detect a 1.3 standard deviation difference in continuous outcome measures and a 38% absolute difference in proportions (assume base rate of 50%). This pilot study will also provide observed effect size for use in the design of future analysis.

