#### 12.7 \* Primary Outcome(s)

Indicate which **variable(s)** will be assessed to judge the primary specific aim. Give measurement units, if applicable.

Total number of colonic submucosal neurons and glia cells in humans before and after course of antibiotics.

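### Section 12.11's claim of over 80% power for a 38-point difference in proportions is not met by any paired test on 10 participants, and no listed outcome is binary

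*Combined protocol and SAP*

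**What the plan says.** Section 12.10 names a single analysis: "we will assess the change in the outcomes between baseline and follow up using a paired sample t-test", "holding Type I Error to 5"%. It does not say whether the test is one- or two-sided.

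Section 12.11 then justifies the sample size. It begins "Assuming we can enroll 10 patients" and continues "we will have over 80% power to detect a 1.3 standard deviation difference in continuous outcome measures". The same sentence adds a second claim: "and a 38% absolute difference in proportions (assume base rate of 50"%). No test, sidedness or within-person agreement is given for that second claim.

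The primary outcome in 12.7 is a count: "Total number of colonic submucosal neurons and glia cells in humans before and after course of antibiotics". The secondary outcomes in 12.8 are gene expression profiles, metabolite changes and "Gut microbiota changes in humans after course of antibiotics". None is defined as a yes/no result per participant.

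**The concern.** Ten people give very little information on a yes/no outcome, so over 80% power for 50% against 88% is a surprising claim. It is more surprising when the comparison is within person, because only participants whose status changes contribute to the test. The claim is also one of the two operating characteristics offered to the IRB in support of n = 10.

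What is at stake is the accuracy of that justification. If a yes/no variable were added at analysis, a null result could be read as evidence against a 38-point effect. The figure could also be copied into a later design, since 12.11 says the pilot will inform future work.

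**Working it through.** **Inputs.** From the plan: n = 10, each measured before and after; base rate 0.50; difference 0.38, so 0.50 against 0.88 (a fall to 0.12 is symmetric); alpha 0.05, taken from 12.10. Assumed, because not stated: two-sided testing, with one-sided also shown; and the probability p10 that a participant changes in the reverse direction. For 0.50 to 0.88, p10 can lie anywhere from 0 to 0.12. The forward-change probability is p01 = p10 + 0.38.

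**1. Trying to reproduce the plan's figure (one sample against a fixed 50%).**

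- Score: Φ[(0.38 − z·√(0.25/10)) / √(0.88·0.12/10)] = Φ[(0.38 − z·0.1581)/0.1028]. This gives 75.2% two-sided (z = 1.96) and 87.8% one-sided (z = 1.645).
- Arcsine: Φ[(2.4341 − 1.5708)·√10 − z]. This gives 77.9% two-sided and 86.1% one-sided.
- Wald with the alternative variance: Φ[0.38/0.1028 − z]. This gives 95.9% two-sided.

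The smallest difference detectable with 80% power, two-sided, is 38.7 points (arcsine) or 39.2 points (score). So 38 points is close to, but not inside, what these two approximations give.

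The exact binomial shows what lies behind the results above 80%. Rejecting at 8 or more of 10 has power P(X ≥ 8 | 0.88) = 89.1%, but its one-sided alpha is P(X ≥ 8 | 0.5) = 5.47% (10.9% if the mirror-image rule is added). Holding 5% requires 9 or more of 10, where alpha is 1.07% one-sided and power is **65.8%**.

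**2. The test that matches the design: McNemar on 10 pairs.** Let b be the number of forward changes and c the number of reverse changes. Power is the sum of the multinomial probabilities of every (b, c) that rejects. With p10 = 0 it can be followed by hand, because c = 0 and b is binomial(10, 0.38):

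- Exact, two-sided: needs b ≥ 6 (2·0.5⁶ = 0.031; b = 5 gives 0.0625). Power 13.5%.
- Mid-p, two-sided: needs b ≥ 5. Power 31.8%.
- Asymptotic, two-sided: needs b ≥ 4 (z = √4 = 2.00). Power 56.6%.
- Asymptotic, one-sided: needs b ≥ 3 (z = √3 = 1.73). Power 79.8%.

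Full enumeration, two-sided 5% unless marked:

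| p10 | Exact | Mid-p | Asymptotic | Asymptotic, one-sided |
|---|---|---|---|---|
| 0 | 13.5% | 31.8% | 56.6% | 79.8% |
| 0.03 | 15.4% | 32.1% | 50.4% | 66.8% |
| 0.06 | 16.6% | 31.4% | 43.7% | 56.4% |
| 0.12 | 17.2% | 28.3% | 32.3% | 44.4% |

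Applying the plan's own paired t-test to the 0/1 changes gives the same power as the asymptotic columns. The most favourable cell, one-sided with no reverse changes, is still not over 80%.

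**3. Two-group readings, two-sided.** Ten against ten: 45% (normal approximation), 25% (Fisher). Five against five, since 12.9 mentions two matched groups of five: 23% and 11%.

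**4. The companion claim.** Paired t-test with n = 10 and d = 1.3 SDs of the differences: noncentrality 1.3·√10 = 4.11, critical value 2.262 on 9 df, power 95.4%. That claim holds on this reading of the SD.

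**The case against.** The strongest reply is that the clause names neither a test nor a side, and that a stated base rate of 50% fits a one-sample comparison with a fixed value. On that reading the one-sided approximations give 86–88% and the two-sided Wald formula gives 96%. A reader might therefore be tempted to say that the figure fails under every usual test. That goes too far, and the documents do not support it. What remains is that these approximations replace each participant's measured baseline with a constant, and that their rejection rule at n = 10 exceeds the 5% promised in 12.10.

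Two further inferences should be avoided. One is that exact McNemar needs all changes to go the same way. It needs at least 6 changes, but 8 against 1 (p = 0.039) and 9 against 1 (p = 0.021) are also significant. The other is that the true power is about 15%. That depends on choosing the exact test and on a discordance the plan never gives; across two-sided versions the range is 13–57%.

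It can also be said that nothing turns on the clause. Section 12.10 calls the study a pilot and exploratory, 35.2 ticks only the exploratory box, enrolment is closed according to 12.9, and the continuous claim supports n = 10 by itself. This stands, and it limits the severity. It does not make the number right.

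The cell-type proportions mentioned under the laboratory procedures in 12.9 do not supply a use for the clause. They are fractions within tissue, expected to be small, not event rates across ten people. The stool questionnaire is neither a listed outcome nor dichotomised.

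**Conclusion.** The stated property is wrong for the planned before/after comparison. Against a claimed power of over 80%, two-sided McNemar power is 13–57% depending on the version of the test and on p10 between 0 and 0.12. No paired version reaches 80% even one-sided. For 80% two-sided power at 38 points, the usual McNemar sample-size formula needs about 19 pairs at p10 = 0, 25 at 0.06 and 32 at 0.12.

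The claim also corresponds to no outcome in 12.7 or 12.8. A reader might infer that the sample size as a whole is unjustified. The documents do not support that: the 1.3 SD statement matches the planned paired t-test and the count-type primary outcome, provided the SD is that of the within-person differences, which 12.11 does not say. Severity is minor to moderate.

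**What to change.** Delete the proportions clause from 12.11. Let n = 10 rest on the 1.3 SD statement, and add that the SD is that of the within-person differences (power 95% by paired t-test, two-sided 5%).

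If a yes/no outcome is wanted, name it in 12.8. State which paired test will be used, its sidedness and the assumed discordance, and restate the power for that test. Report the result descriptively with an exact confidence interval.

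The cost is one or two sentences and the loss of a favourable figure. No visit, procedure, participant or planned analysis changes.
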